2.2 Step 2: Localiser sequences and planning

The localizer sequences used and brain field-of-view (FOV) positioning technique used may be adapted from established local protocols and auto-alignment functions may be used where available. However, in positioning the diagnostic axial scans it is essential that:

1. Identical slice positioning is used for all 4 diagnostic sequences.

2. The FOV is aligned in all 3 planes to achieve a true anatomical axial plane.
3. The axial slices align parallel to the anterior commissure-posterior commissure plane (ac-pc plane)
4. The scans cover the whole brain from at least vertex to foramen magnum.

For those units without established procedures for planning axial brain imaging, an example protocol is provided below. Sample parameters are provided in Table 1.

Step A: 3 plane localizer

Step B: Limited FOV sagittal T1 weighted images planned from coronal and axial localizers with the center slice aligned to the sagittal midline structures in both planes (**Figure 1**).

[figure not shown]

Figure 1. 3 plane localiser used for planning T1 weighted sagittal images. The centre slice is aligned to the sagittal midline structures on the coronal (A) and axial (B) images. Note that the sagittal images are for planning only and do not need to cover the whole brain in the axial and coronal planes.

Step C: Slices for the axial sequences are angled parallel to ac-pc plane (**Figures 2 & 3**) and the FOV covers the whole brain. The center slice should have the same position for all 4 diagnostic scans.

[figure not shown]

Figure 2. T1 weighted sagittal localizer (left) plus coronal and axial images from previous 3-plane localizer used for planning the 4 axial diagnostic sequences. The ac-pc plane is planned from the mid sagittal images.

[figure not shown]

Fig 3. Locating the ac-pc line. The anterior commissure (ac) (red dot), the posterior commissure (pc) (yellow dot). The ac-pc line passes from the superior surface of the ac through the center of the pc (purple horizontal line). ref:http://ccn.ucla.edu/wiki/index.php/Find_the_AC-PC_line

Table 1. Example parameters for the planning sequences

Sequence	3 plane localiser			Sagittal planning sequence
	Sagittal	Axial	Coronal	
Orientation	Sagittal	Axial	Coronal	Sagittal
Phase encode direction	A-P	A-P	R-L	A-P
In-plane FOV in mm (RL x AP)	260 x 260			240 x 240
Slices	5			19
Slice thickness (mm)	8			5
Interslice gap (mm)	2			1.5
True in-plane resolution (mm)	1.4 x 1.0			0.9 x 0.9
TR (ms)	7			195
TE (ms)	2.95			4.76
Averages	2			1
Estimated acquisition time	42 sec			29 Ec

2.3 Step 3: Diagnostic Sequences

All 4 sequences are performed in the axial plane, with identical slice positioning and in the order below. Mandatory sequence parameters that must be used are provided in **table 2**.

1. Diffusion weighted imaging (DWI)
2. T2-weighted turbo spin echo (T2w TSE or equivalent)
3. T2-weighted gradient echo (T2*w GRE or equivalent)
4. Fluid attenuated inversion recovery (FLAIR or equivalent)

[figure not shown]

Figure 4. Examples of images from the 4 diagnostic axial sequences

Table 2. Mandatory parameters for 4 diagnostic sequences

Sequence	DWI	T2w TSE (or equivalent eg FSE)	T2w GRE (or equivalent eg FLASH)	T2w FLAIR (or equivalent eg TIRM)
Orientation	Axial	Axial	Axial	Axial
Acquisition type	2D (multislice)	2D (multislice)	2D (multislice)	2D (multislice)
Phase encode direction	A-P	R-L	R-L	R-L
In-plane FoV in mm (APxRL)	240 x 240	240 x 180	240 x 240	240 x 180
Slices	39 or full head	29	29	29
Slice thickness (mm)	4	5	5	5
Interslice gap (mm)	0	0.75	0.75	0.75
Acquisition matrix (frequency x phase)	192 x 192	512 x 288	256 x 256	256 x 192
True in-plane acquisition resolution (frequency x phase mm) ¹	1.3 x 1.3	0.5 x 0.6	0.9 x 0.9	0.9 x 0.9
TR ²	4500	5040	997	8000
TE ²	89	93	26	89
TI ²				2370
Averages	4	2	1	1
Flip angle (deg)		150	20	150
Turbo factor (TSE)		16		16
DWI b values (mm s ⁻²)	0 and 1000			
Diffusion directions	3			
RF pulse type	Normal	Normal	Normal	Normal
Estimated acquisition time	1 min 27	3 min 08	4 min 17	3 min 30

¹Reconstruction resolution may be higher with interpolation.

²Timing parameters may be set to the closest allowed value, if the scanner only allows changes on certain steps.

[figure not shown]
2.4 Step 4: Assess Images for Quality

- All images should be checked for quality before the patient is moved from the scanner. Sequences degraded by artefacts such as excessive movement should be repeated immediately if at all possible.
- The reason for degraded images or incomplete scans to be noted in the data transmission form.

2.5 Step 5: Image Post Processing

- The DWI dataset is processed to provide:
 - a. b0 images
 - b. b1000 diffusion trace images. This may be combined with the b0 images in a single set of all 26 b0 slices followed by all 26 b1000 trace images. Please do not supply as alternating b0, b1000 images at each slice position.
 - c. Apparent diffusion coefficient (ADC) map

Please note that many scanners can perform this as an automated task

2.6 Step 6: Prepare Data for Submission

All MRI data will be sent to the data center for independent study analysis.

- Data should be stored in DICOM 3.0 format, not DICOMDAT.
- It is important to note that images from the same “B value” (B 0 or no diffusion weighting, B 1000 or heavy diffusion weighting) DWI images need to be sent so that all of the B 0 images are sent in anatomical order (i.e. B 0 slice 1 followed by B 0 slice 2, B 0 slices 3, etc.) followed by the B 1000 images in anatomical order. B 0 images and B 1000 images should not be interleaved.
- All available images must have patient identifiers (protected health information (PHI) such as name, date of birth, medical record number) removed at time of image transfer to the data center.
- Please use the following during anonymization:

- **Modality** = MR
 - **“Body Part Examined”** contains the value = HEAD
 - **“Protocol Name”** contains any of the values = PWI, Brain, Neuro, Perf.
 - **“Series Description”** contains any of the values = DWI, T2 FLAIR, T2 GRE, T2 TSE, LOC etc.
- Imaging studies should be labeled as followed: **CCSCTC-SNR**
CC- is the region ID which will be assigned in two letter format (e.g US, UK).
SC- is the site ID which will be assigned in two number format (01, 02, etc.).
TC- is the internal ID which will be assigned in two number format (for REFLECT this number is 09).
SNR- is the subject number which will be assigned in three number format (001, 002, etc.)
 - It should be clearly stated in the data transmission form or the uploading system the protocol time point of the study. However, this information must NOT be incorporated into the DICOM image headers themselves. (i.e. it should not be included in the patient identifier, protocol name, study comment or similar fields).
 - Make sure all required images are included:
 1. Localiser images
 2. Axial DWI: to include b0, b1000 trace images and ADC map
 3. Axial T2w TSE
 4. Axial T2*w GRE
 5. Axial T2w FLAIR

Instructions for submission of MRI imaging data will be reviewed with each site during DW-MRI Protocol Training sessions. Images will be sent via electronic transfer using the dedicated transfer solution.

Instructions will be provided during site set-up. You may also reference the transfer solutions Site User Guide and/or the Quick Reference Sheet for specific instructions regarding the electronic transfer of MR images.

3.0 MRI Precautions and Considerations

Standard precautions should be taken into consideration for any patient undergoing MR imaging. Patients should be assessed for history of implantable devices that may have occurred as a result of, or outside of the conduct of the REFLECT Trial. This may include, but is not limited to the following:

- Permanent pacemaker implantation

- Implantable Cardioverter-defibrillator
- Surgical clips or other devices implanted as a result of vascular injury or other complication requiring surgical intervention
- Aortic bioprosthetic valve implanted at the time of trial enrollment for the treatment of senile aortic stenosis

Considerations and precautions for commercially available aortic transcatheter bioprosthetic valves that may be utilized for patients enrolled in the REFLECT Trial:¹

Edwards SAPIEN 3 Transcatheter Heart Valve²

Edwards Life Lifesciences Corporation, Edwards Lifesciences LLC Irvine California, USA

Non-clinical testing has demonstrated that the Edwards SAPIEN THV (implant) is MR compatible. It can be scanned safely under the following conditions:

- Static magnetic field of 1.5 Tesla (T) or 3 Tesla. Use of 3 Tesla is not allowed per the REFLECT protocol
- Spatial gradient field of 2500 Gauss/cm or less.
- Maximum whole-body-averaged specific absorption rate (SAR) of 2W/kg for 15 minutes of scanning.
- Normal mode operation, as defined by IEC 60601-2-33 Ed.3.0, of the MR system.

In non-clinical testing and analysis, the implant was determined to produce a temperature rise of less than 1.1°C above background for a whole body SAR of 2.0 W/kg for 15 minutes of MR scanning in a 1.5T cylindrical whole body MR system, assessed using a GE Signa whole body coil and a phantom designed to simulate human tissue. The phantom average SAR calculated using calorimetry was 2.2 W/kg and local background SAR at the site of the implant was 5.6 W/kg. The measured rise above background was 0.7°C for a whole body SAR of 2 W/kg in a 3.0T cylindrical bore whole body MR system, assessed using a GE Signa HDx whole body active shield MR scanner with software version 14/LX/MR and a phantom designed to simulate human tissue. The phantom average SAR calculated using calorimetry was 2.9 W/kg and local background SAR at the site of the implant was 8.4 W/kg.

The image artifact extended as far as 15mm from the implant for spin echo images and 40mm for gradient images when scanned in non-clinical testing in a 3.0T GE signa HDx MR system. The implant has not been evaluated in MR systems other than 1.5 or 3.0T.

Medtronic CoreValve® Family of THV (Including Evolut R and Evolut Pro)

Medtronic CoreValve LLC

1.5 Tesla

¹ Information ascertained from manufacturer's Instructions For Use (IFU) available in the public domain as of 03 November 2011. Precautions for specific devices should always be referenced using the manufacturer's current IFU.

²Edwards Lifesciences LLC, Web IFU 199473001A

<http://www.fda.gov/downloads/AdvisoryCommittees/CommitteesMeetingMaterials/MedicalDevices/MedicalDevicesAdvisoryCommittee/CirculatorySystemDevicesPanel/UCM262938.pdf>

Based on non-clinical testing and modeling, a 26 mm bioprosthesis was calculated to produce a temperature rise of less than 3.5°C at a maximum whole body averaged specific absorption rate (SAR) of 2.0 W/kg for 15 minutes of MR scanning in a 64 MHz whole body transmit coil, which corresponds to a static field of 1.5 Tesla.

3.0 Tesla

Based on non-clinical testing and modeling, a 26 mm bioprosthesis was calculated to produce a temperature rise of less than 3.6°C at a maximum whole body averaged specific absorption rate (SAR) of 2.0 W/kg for 15 minutes of MR scanning in a 128 MHz whole body transmit coil, which corresponds to a static field of 3.0 Tesla.

1.5 and 3.0 Tesla

The bioprosthesis should not move or migrate when exposed to MR scanning immediately after implantation. MRI of at least 3 tesla and 1.5 tesla may be performed immediately following the implantation of the bioprosthesis. The magnetic force on the bioprosthesis-determined at a location where the magnitude of the magnetic field strength was about 1.5 tesla and the magnitude of the spatial gradient of the magnetic field was about 400 gauss/cm – was determined to be less than 5% of its weight. Non-clinical testing at field strengths other than 1.5 tesla and 3.0 tesla has not been performed to evaluate bioprosthesis heating.

MR image quality may be compromised if the area of interest is in the same area, or relatively close to the position of the device. It may be necessary to optimize the MR imaging parameters for the presence of the implant. When tested at 3.0 tesla, the image artifact extended less than 3 mm beyond the bioprosthesis for the spin echo sequence with TR = 500 ms and TE = 20 ms and less than 7 mm beyond the bioprosthesis for the gradient echo sequence with TR = 100 ms and TE = 14.4 ms and flip angle = 30°. The mid region of the device lumen was obscured.

1.0 Background

Cardiac Multi-Detector Computed Tomographic Angiography (Cardiac MDCT Angiography) is intended to evaluate aortic valve anatomy, aortic root dimensions for prosthetic valve sizing, and assessment of the aorta and peripheral vessels for anatomy and disease burden. The CT scan results will be used for assessment of the aortic arch for compliance with positioning of Keystone Heart TriGuard™ as well as planning the best fluoroscopy angle for the procedure. Assessment of the ileo-femoral arteries will indicate if the peripheral arteries anatomy can accommodate the TriGuard delivery system.

2.0 Equipment

- Multi-detector CT scanner (64-slice minimum) with ECG-gating capability.
 - The scans submitted for analysis of the aortic root should be ECG-gated; non-gated scans in areas with cardiac motion lead to measurement inaccuracy and therefore incomplete information for device selection.
 - Abdominal aorta and peripheral vessel image acquisition may be non-gated.
- Dual-source scanner preferred due to enhanced temporal resolution and reduced motion artifacts.

3.0 Scans

- 1) Chest Topogram.
- 2) Prospective ECG-gated non-contrast scan of aortic root and thoracic aorta.
- 3) Retrospective ECG-gated contrast enhanced scan of the aortic root and thoracic aorta, immediately followed by non ECG-gated contrast enhanced scan of the abdominal aorta and peripheral vessels.*

*If CT scanner is incapable of sequential ECG-gated to non-ECG gated scan, the contrast enhanced CT study can be performed using retrospective ECG-gating in its entirety.

4.0 Scanning Procedures

The optimal scan is similar to a coronary calcium score scan followed by a CT coronary angiogram / aortogram. The aim is to first evaluate the degree of calcification in the aortic valve, and then to obtain adequate contrast in the following regions of interest: endo-luminal surface for visualization of left heart, aorta, and peripheral access vessels (i.e., femoral arteries). Temporal resolution should be optimized to reduce motion artifact. Spatial resolution should be as high as possible (goal is smallest isotropic voxel size).

4.1 Step 1: Patient Preparation

- Administer medication per institution standard practice for CT scanning.
- Attach ECG electrodes for gating of scan. Verify quality of ECG tracing on scanner console.
- Prepare intravenous line for administration of contrast media.
- Assess heart rate variability during breath-hold.

4.2 Step 2: Chest Topogram

- A chest topogram can be used to plan subsequent imaging.

[figure not shown]

Figure CTA-1: Example image of chest topogram

4.3 Step 3: Prospective ECG-gated non-contrast scan of aortic root

The aim of this scan is to quantify the extent of calcium in the aortic valve and aorta, equivalent to scans calculating a coronary calcium score (e.g. Agatston score).

1. The submitted scan should cover the area from the temporal-mandibular-joint (TMJ) to the diaphragm to encompass the entire heart, aortic arch and thoracic aorta.
2. Prospective ECG-gating with sequential slice acquisition is preferred.
3. Scan at peak voltage of 120kVp with tube current of 140-150 mAs tube current.
4. Slice thickness 2.5-3.0 mm with a pitch of 1.

4.4 Step 4: ECG-gated contrast enhanced scan of the aortic root and thoracic aorta, and non-ECG gated contrast enhanced scan of abdominal aorta and peripheral vessels

The aim of this scan is to assess the anatomy of the aortic root, aortic arch and cerebral vessels, thoracic / abdominal aorta, and peripheral vessels (please refer to Table 1 below for suggested parameters).

1. The optimal scan would include the area from the temporal-mandibular-joint (TMJ) to the mid-thigh, using dynamic 4D acquisition and retrospective ECG-gating from the TMJ to the diaphragm (to evaluate the aortic root, aortic arch, cerebral vessels and thoracic aorta), followed by a non-ECG-gated scan from the diaphragm to the mid-thigh (to evaluate the abdominal aorta and peripheral vessels). If a sequential ECG-gated/non-ECG gated study is not available, the entire study could be performed using retrospective ECG-gating.
2. Detector collimation is 0.4-0.625mm.
3. Slice thickness is $\leq 0.8\text{mm}$.
4. Peak voltage of 120kVp with tube current from 350-550 mAs per scanner protocol for patient body mass index.

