necessary for TAVI, make dislodgement of aortic debris more likely.²⁶ Second, disruption of aortic valvular and annular calcification during TAVI is an additional source of embolic material; procedural transcranial Doppler monitoring indicates that the valve itself is the primary source of cerebral emboli following TAVI, and that most emboli are composed of debris dislodged during direct manipulation of the calcified aortic valve and crushing of the leaflets and aortic annulus during implantation.²⁷

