- A 12-lead electrocardiogram. An ECG performed within 30 days prior to the procedure may be used as the baseline ECG provided there have been no signs or symptoms of myocardial ischemia between the time of the ECG and enrollment (in which case the ECG should be performed within 24 hours prior to enrollment).
- CT imaging (standard and contrast-enhanced angiography preferred) of the left heart, aorta, great vessels, and peripheral access vessels performed up to 1 year prior to the procedure should be submitted for review.
- NIH Stroke Scale (NIHSS) up to 14 days prior to procedure. Neurologic status evaluation using the NIH stroke scale shall also be performed 2-5 days post-procedure and during each follow-up assessment. The examination must be performed by a neurologist, or a clinical designee (e.g. neurology fellow).
- Modified Rankin Scale (mRS) up to 14 days prior to procedure. The mRS will also be performed 2-5 days post-procedure and during each follow-up assessment. The assessment must be performed by a neurologist or a clinical designee (e.g. neurology fellow).
- A full neurological evaluation should be performed by a neurologist in all patients in whom a stroke or TIA is suspected on the basis of the NIHSS, mRS, or other signs or symptoms.
- A neuropsychological test battery (§16.7) will be administered up to 30 days prior to procedure by a qualified individual, and will be re-administered 2-5 days post-procedure and at 30 and 90 days. The test battery includes: (Phase I only)
 - Montreal Cognitive Assessment (MoCA) - A cognitive screening instrument that includes tasks that assess attention and concentration, executive functions, memory, language, visuoconstructional abilities, abstraction, calculations, and orientation. It takes approximately 10 minutes to administer and is available in several languages.
 - Repeatable Battery for the Assessment of Neuropsychological Status (RBANS) - A comprehensive, but brief, neuropsychological battery that includes assessment of immediate memory, visuospatial/constructional abilities, language, attention, and delayed memory. The RBANS is available in many different languages and typically takes less than 30 minutes to administer. Alternate forms of the tests are used for repeat testing.

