No imputation of missing DW-MRI data will be performed for the primary analysis. However, in order to assess the sensitivity of results to missing DW-MRI data, multiple imputations with the linear regression approach will be used as the secondary sensitivity analysis. This assessment is necessary because the rate of permanent pacemaker implantation (causing loss to DW-MRI follow-up) may vary according to patient clinical characteristics and prosthesis type.¹⁰⁶ Specifically, missing total volume of cerebral ischemic lesions on post-procedure diffusion-weighted MRI will be imputed via multiple imputation linear regression (10 imputed data sets will be created). The covariates used for the imputation model will be treatment group, age at time of enrollment, body mass index, race, smoking status, creatinine level, hyperlipidemia, hypertension, aortic arch disease burden, porcelain aorta, aortic valve area at baseline, procedure time, country, valve type, balloon post dilatation, arch type, and level of calcification. This creation of the 10 datasets will be carried out using PROC MI in SAS. For each data set, the above-mentioned chi-square test will be carried out on the primary endpoint and one overall chi-square result will be generated from the 10 datasets. For each patient with missing TLV, the crux of multiple imputation is to estimate TLV from patients with non-missing TLV who have similar baseline characteristics as the patient with missing TLV. Thus, in essence, TLV for high risk patients with missing TLV due to pacemaker will theoretically be estimated from patients with similar high risk profiles who do not have pacemakers.

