- Operative risk (by Society of Thoracic Surgeons [STS] Risk Score)
- Type and duration of antiplatelet therapy:
 - Pre- and peri-procedural therapy:
 - Protocol-recommended antiplatelet therapy vs. other
 - Maintenance therapy:
 - Dual antiplatelet therapy (DAPT) to 90 days vs.
 - Monotherapy (aspirin or clopidogrel) to 90 days vs.
 - Warfarin with antiplatelet therapy to 90 days vs.
 - Other

As above, analysis of variance on the cube root transformation for total lesion volume data and logistic regression for death/stroke and NIHSS worsening will be used, and a 0.15 level of significance will be used to assess the significance of the interaction.

If the primary efficacy endpoint is met in the primary (eITT) analysis population, sequential testing of the primary efficacy hypothesis will be conducted in the ITT analysis population of evaluable subjects (Roll-In patients are excluded.) As a secondary analysis, the primary efficacy endpoint and its components will be evaluated in the ITT analysis population of evaluable subjects (Roll-In patients are excluded). As an additional analysis, the primary efficacy endpoint will be evaluated in the PT population of subjects with available data.

An additional analysis of the primary efficacy endpoint will also be performed in the primary eITT analysis population with adjustment for pre-existing cerebral lesion volumes. The adjustment will be performed using a quantile regression with the resultant score being the dependent variable and group and the pre-existing cerebral lesion volumes will be independent. Specifically, the PROC QUANTREG procedure will be used to model the median of the score with QUANTILE=0.5 option.

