12.4.5.1.2 Secondary Efficacy Endpoints

- **Imaging Efficacy Endpoints**

All secondary imaging efficacy endpoints will be reported by treatment group in the eITT Population of subjects with available data using descriptive statistics. No formal hypothesis testing will be performed, and there is no plan to adjust alpha to account for multiple testing of exploratory secondary endpoints. Statistics for continuous variables will include mean, median, standard deviation, minimum, maximum, and sample size for each treatment group. Binary variables will be summarized using frequencies, percentages, and sample size for each treatment group.

The eITT analysis will be considered primary. As a secondary analysis, all secondary imaging efficacy endpoints will be evaluated in the ITT population of evaluable subjects. An additional analysis will also be performed in the PT population.

An additional analysis of secondary imaging efficacy endpoints with adjustment for pre-existing cerebral lesion volume will also be performed in the primary eITT analysis population. These endpoints include presence of cerebral ischemic lesions (§□), number of cerebral ischemic lesions (§□), per-patient average single cerebral ischemic lesion volume (§□), single cerebral ischemic lesion volume (§□), and total volume of cerebral ischemic lesions (§□), which vary by their distribution from binary (as in "presence of cerebral ischemic lesions") to Poisson, or possibly negative binomial in others. The choice of a specific model used for adjustment will therefore depend on the actual distribution of the dependent variable (logistic, log-linear, Poisson, negative binomial or quantile). The models will include the study group and pre-existing cerebral lesion volume as independent variables.

- **Neurologic Efficacy Endpoints**

All secondary neurologic efficacy endpoints will be reported by treatment group in the eITT Population of evaluable subjects (Roll-In subjects are excluded) using descriptive statistics. No formal hypothesis testing will be performed, and there is no plan to adjust alpha to account for multiple testing of exploratory secondary endpoints. Statistics for continuous variables will include mean, median, quartiles, standard deviation, minimum, maximum, and sample size for each treatment group. Binary variables will be summarized using frequencies, percentages, and sample size for each treatment group.

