4.5 Step 5: Submission of CT data

All available CT data should be sent electronically to the data center (Core Laboratory).

- Data should be stored in DICOM 3.0 format, not DICOMDAT.
- Submitted images must have patient identifiers (protected health information (PHI) such as name, date of birth, medical record number) removed at time of image transfer to the data center.
- Please use the following during anonymization:

- **Modality** = CT
- **“Body Part Examined”** contains the value = CHEST
- **“Protocol Name”** contains any of the values = PWI, Brain, Neuro, Perf, Low Grade
- **“Series Description”** contains any of the values = CHEST TOPOGRAM, ECG NON CONTRAST AORTIC ROOT, ECG CONTRAST AORTIC ROOT, ECG CONTRAST THORATIC AORTA, NON ECG CONTRAST ABDOMINAL AORTA NON ECG CONTRAST PERIPHERAL VESSELS.
- Submitted imaging studies should be labeled as follows: **CCSCTC-SNR**
 - CC-** is the region ID which will be assigned in two letter format (US or UK).
 - SC-** is the site ID which will be assigned in two number format (01, 02, etc.).
 - TC-** is the internal ID which will be assigned in two number format (for REFLECT the number is 09).
 - SNR-** is the subject number which will be assigned in three number format (001, 002, etc.)
- Please provide all the following images if available:
 - Chest Topogram
 - ECG-gated non-contrast scan of aortic root and aortic arch
 - ECG-gated contrast enhanced scan of aortic root and thoracic aorta, immediately followed by non-ECG-gated contrast scan of abdominal aorta and peripheral vessels

Instructions for submission of CT imaging data will be reviewed with each site during CT Protocol Training sessions. Images will be sent via electronic transfer using the transfer solution.

Instructions will be provided during site set-up. Reference the transfer solutions Site User Guide and/or the Quick Reference Sheet for specific instructions regarding the electronic transfer of CT images.

Table 1. Suggested Scan Parameters for contrast enhanced scan of aortic root, aorta and peripheral vessels

	Dual-Source CT	Single-Source CT
IV injection with iodine contrast	100-120 (320 mg/ml or higher)	
Injection Rate	4-5 mL/s	
Bolus tracking, delay	Delay time calculated using protocol for current scanner (bolus tracking, etc.) with triggered by contrast concentration >100 HU in the high descending aorta	
ECG Leads	Required	
ECG-gating	Retrospective ECG-gating from TMJ to diaphragm; then non-ECG-gating from diaphragm to mid-thigh	

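### The plan uses baseline calcification and arch disease burden to predict lesion volume when imputing it, but adjusts no efficacy comparison for them

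*Combined protocol and SAP*

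**What the plan says.** **Measurement.** The CT appendix (16.10, Background) gives as one purpose of the scan "assessment of the aorta and peripheral vessels for anatomy and disease burden". For the non-contrast scan (its section 4.3) it adds: "The aim of this scan is to quantify the extent of calcium in the aortic valve and aorta". Under 7.2, CT "performed up to 1 year prior to the procedure should be submitted for review". Under 6.2.1 and 11.1, the core-laboratory CT analysis goes to the Patient Review Committee before a subject can be randomised. The submission instructions are softer: "Please provide all the following images if available".

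**Link to outcome.** Section 4.1.2.1 states that "disruption of aortic valvular and annular calcification during TAVI is an additional source of embolic material". In 12.4.3, the multiple-imputation model for missing total lesion volume includes "aortic arch disease burden, porcelain aorta, aortic valve area at baseline", and also arch type and level of calcification.

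**Treatment comparisons.** The adjusted primary analysis in 12.4.3 is a median regression of the score in which "group and the pre-existing cerebral lesion volumes will be independent". For the secondary imaging endpoints, 12.4.5.1.2 says: "The models will include the study group and pre-existing cerebral lesion volume as independent variables". The neurologic models follow the same pattern. The total-lesion-volume test in 12.2.1.1.3 is a two-sample z-test without covariates. The centre, region, sex, valve, STS-risk and antiplatelet models in 12.4.3 check interaction or poolability, and none contains calcification.

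**The concern.** A plan that relies on calcification and arch burden to predict a missing lesion volume expects to hold those variables and expects them to carry information about the outcome. It gives no reason for leaving them out of every comparison of that outcome between groups.

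Lesion volume varies widely between subjects. The historical figure in Table 6 is 2.18 cm³ with SD 4.5. Lesion volume also decides Tiers 3 and 4 of the primary endpoint and is the last gated secondary endpoint. Adjusting for a baseline predictor reduces residual variance and corrects chance imbalance in embolic source, which is useful with about 75 concurrent controls.

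The 63 Phase I controls may also be pooled. They were not randomised against TriGUARD 3 and were enrolled under somewhat different anatomic and access criteria (6.1.2), so balance on embolic source is not assured for them.

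**Working it through.** **The plan's own figure.** Section 12.2.4 gives more than 80% power for 150 v 75 and at least 92% with 138 controls, at one-sided 0.025. A Monte Carlo check of the Finkelstein-Schoenfeld test used the stated tier rates, the 15% or 50 mm³ win rule, 15% MRI loss and a 30% reduction within each volume category. It assumed uniform volumes within category, a top category capped at 500, 1000 or 3000 mm³, and 600 replicates per setting. It gives 82–93% for 150 v 75 (142 v 71 after 5% loss) and 92–99% for 150 v 138 (142 v 131). The stated power is reproduced, and it does not depend on calcification.

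**Generic gain from adjustment.** Let R² be the share of outcome variance explained by the added covariates. The documents give no value, so a range is shown. The standard error is multiplied by √(1−R²), the equivalent sample size is 225/(1−R²), and power from an 80% start is Φ((1.960 + 0.842)/√(1−R²) − 1.960).

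| R² | SE multiplier | Equivalent N | Power |
|---|---|---|---|
| 0 | 1.000 | 225 | 80.0% |
| 0.01 | 0.995 | 227 | 80.4% |
| 0.05 | 0.975 | 237 | 82.0% |
| 0.10 | 0.949 | 250 | 84.0% |
| 0.20 | 0.894 | 281 | 87.9% |

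This is a large-sample result for a comparison of means. It illustrates scale only. The 225 subjects and 80% belong to the primary test, which the fix leaves alone, and the adjusted primary analysis is a median regression, to which the formula does not directly apply.

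**The planned raw-volume z-test.**
- Inputs: mean 2.18 and SD 4.5 cm³ (Table 6), an assumed 30% lower mean on device, and 15% MRI loss, giving 127.5 v 63.75 scanned.
- Difference: 0.30 × 2.18 = 0.654.
- SE: 4.5 × √(1/127.5 + 1/63.75) = 0.690.
- Unadjusted power: Φ(0.654/0.690 − 1.960) = 15.6%.
- Dividing the ratio 0.947 by √(1−r²) gives 0.967, 0.993 and 1.034 for r = 0.2, 0.3 and 0.4. Power is then 16.0%, 16.7% and 17.7%, a gain of about 0.5 to 2 points.
- With Table 5's figures, which exclude strokes where possible (1.49, SD 2.18), the same sum runs from 26.7% to 27.6%, 28.8% and 30.8%.

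**How often the gated volume test is reached.** It is fifth in the sequence. NIHSS worsening, second, is assumed at 9% v 6%. For 150 v 75, SE = √(0.06×0.94/150 + 0.09×0.91/75) = 0.0383 and power = Φ(0.03/0.0383 − 1.960) = 12%. With 138 controls it is 16%. Under the plan's assumptions the volume test is therefore reached in at most about one trial in six. A gain in precision matters mainly for the estimates in the supportive analyses.

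**The case against.** The case against has several parts, and much of it stands.

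- **No graded calcium variable is assured.** A reader might infer from the scan's stated aim that every subject already has a calcium grade. The documents do not support this. The aim stands in an acquisition guideline, images are requested only where available, CT may be up to a year old, and no calcium score is defined as a core-laboratory output. The imputation list gives no site, scale or source for level of calcification, so taking it from CT is itself an inference.
- **Missingness may follow phase.** The version history adds the CT core laboratory in September 2016, while the timeline starts Phase I enrolment in June 2016. If early Phase I controls lack core-laboratory reads, a category for unavailable CT would be tied to phase and hence to treatment in the pooled comparison.
- **Strength of prediction is not shown.** The imputation list also holds body mass index, race and procedure time, so being on it does not prove prognostic value. Excluding heavily calcified arches (6.1.2.1.15) narrows the range and could bring the gain close to zero.
- **The unadjusted tests are valid.** Among concurrently randomised subjects, chance imbalance is already covered by the type I error rate. Most of the models at issue are exploratory.
- **A covariate has already been chosen.** This is true, but Tables 7 and 7a schedule cerebral MRI only after the procedure. If pre-existing lesion volume is read from that scan, it is missing for the same subjects who lack DW-MRI. Baseline CT variables do not have that limitation.

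These points limit the size and certainty of the gain. They do not explain why variables used to impute the outcome are absent from every comparison of it.

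**Conclusion.** The point holds as a modest, low-cost improvement. The plan names baseline calcification and arch-burden variables as predictors of total lesion volume for imputation, and no efficacy treatment comparison adjusts for them.

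The gain cannot be fixed from the documents. On the generic 80% illustration it is about 0.4 points at R² = 0.01, 2 points at 0.05 and 4 points at 0.10. For the planned z-test on raw volume it is about 0.5 to 2 points from roughly 16%, assuming r of 0.2 to 0.4, a 30% lower mean and the Table 6 figures.

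A reader might go further and infer that the lesion-volume comparison is biased, or that the primary test loses a known amount of power. Neither is supported. Among concurrently randomised subjects this is lost efficiency only, and the primary test is not the analysis to be changed. With pooled Phase I controls, imbalance in embolic source is possible, but the documents do not show it, and a poolability assessment is planned.

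Section 12.1 refers further detail to the SAP. This reading rests on the analysis text in section 12.

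**What to change.** 1. Keep the unadjusted Finkelstein-Schoenfeld test as the primary analysis.
2. In the adjusted analyses of 12.4.3 and 12.4.5.1.2, add the baseline variables already on the imputation list (arch disease burden, porcelain aorta, arch type, level of calcification) as prespecified covariates. State the source, anatomical site and scale of each. Do not carry over the procedural items on that list, such as procedure time and balloon post-dilatation, because they arise after randomisation.
3. Add a supportive covariate-adjusted comparison of total lesion volume on the cube-root scale that 12.4.3 already uses.
4. Prespecify how missing CT values are handled, so that no randomised subject is dropped for lack of a scan. Because missingness may follow phase, also report the adjusted result in the concurrently randomised Phase II subjects alone.
5. State that the expected gain depends on an unknown correlation.

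The cost is SAP wording and a few model terms, fixed before unblinding. No new procedure is needed, although the core-laboratory outputs must be confirmed as data fields and some CT values may be missing.
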